7.2.2 General Conventions for Summarization

Summary statistics will consist of the number and percentage of responses or counts at each level for categorical variables (e.g. gender). For continuous variables, the sample size (n), mean, median, standard deviation (SD), minimum, and maximum values will be presented.

All mean and median values will be formatted to one more decimal place than the measured value. Standard deviation values will be formatted to two more decimal places than the measured value. Minimum and maximum values will be presented with the same number of decimal places as the measured value.

The number and percentage of responses will be presented in the form XX (XX.X%).

- All summary tables will include the analysis population sample size (i.e., number of subjects).
- Relative Study Day 0 is defined as the day the patient underwent the study procedure. All study days are determined relative to the day the patient underwent the study procedure.
- Baseline values will be defined as those values recorded immediately prior to the study procedure.
- Change from baseline for differences will be calculated as follows:

$$\text{Change} = \text{Post-baseline value} - \text{baseline value}$$

- Missing data may have an impact upon the interpretation of the trial data. The primary presentation of the overall primary endpoint results will be based on the observed data with multiple imputation for missing data using SAS PROC MI. A methodology is also defined in this section for addressing missing dates.
- Date variables will be formatted as DDMMYYYY for presentation; SAS Date9. format.

Data from this study, when applicable will be presented in a listing format. All listings will be sorted by patient number and date, as applicable.

7.3 Center Pooling

This is a multi-center clinical study, with standardization of subject enrollment, data entry and Adverse Event reporting. All investigational sites will follow the requirements of a common protocol, data collection procedures and forms. To present the data from this clinical study in a summary form, a comparison of the following variables will be completed to assess the appropriateness of pooling data from across all sites:

- Baseline demographics such as age, and gender

The distributions of the above variables across the sites will be tabulated. To detect site differences, the Kruskal-Wallis test will be used for continuous variables and the Chi-Square test or the Fisher's exact test will be used for categorical variables, depending on variable distribution.

7.4 Handling of Missing, Unused, and Spurious Data and Dropouts

Handling of dropouts and missing data will depend on their frequency and the nature of the outcome measure.

Subjects with missing data that cannot be resolved prior to database lock may not be included in the tabulation and excluded from the summary statistics if deemed necessary; a listing will be compiled identifying the subjects. The number and percentage of subjects with each characteristic will be presented. The tabulation of subjects across the different characteristics and conditions is independent; multiple subjects can have multiple conditions. Results will be presented based on the number of respondents in each category using counts and percentages.

When calculating rates of Adverse Events, missing and partial dates will be handled as follows. If the entire Adverse Event start date is missing, then the procedure date will be used for the start date. If the month and the day of the month are missing but the year is available, and the year is the same as the year of the procedure then the procedure date will be used for the start date. If the year is greater than the year of the procedure, then January 1st will be used for the month and day of the start date. If the day is missing, but the month and year are available, then the 1st will be used as the day of the start date unless the imputed date would be before the procedure in which case the procedure date will be used for the start date of the Adverse Event.

For baseline categorical variables, "unknown" responses will be counted as not having the characteristic and will be included in the denominator. Missing values will not be counted in rate denominators.

Handling of Missing Start-dates for Interventions

Rules for imputing a full date for interventions with incomplete or missing start-dates are addressed below. In the unusual case that the month portion of an intervention start-date is missing but the day portion is not missing, the day portion of the intervention will be assumed to be missing. Likewise, in the case where the year portion of an intervention start-date is missing but the month and/or day portion is not missing, the month and/or day portion of the intervention start-date will be assumed to be missing. All missing portion(s) of the intervention starting dates will be handled using the same rules:

- In the event that the day portion (and only the day portion) of the intervention start-date is missing:
 - If the intervention started in the same month and year as the study procedure, the intervention start-date will be assumed to be the date of the study procedure (i.e., Study Day 0);
 - Otherwise, the intervention start-date will be assumed to be the 15th day of the given month and year, e.g., XX-DEC-2015 ▪ 15-DEC-2015 where XX represents an unknown value.
- In the event that the day and month portion (and only the day and month portion) of the intervention start-date are missing:
 - If the intervention started in the same year as the study procedure, the intervention start-date will be assumed the date of the study procedure (i.e., Study Day 0);
 - Otherwise, the intervention start-date will be treated as June 15th of the given year, e.g., XX-XXX-2015 ▪ 15-JUN-2015.
- In the event that the day, month, and year portion of the intervention start-date are missing, the start-date of the intervention will be assumed to be the date of the study procedure (i.e., Study Day 0).

Note: With the exception of following special cases, this conservative scheme ensures that an intervention with a partially or completely missing start-date will be treated as post-procedural.

Special Cases on Missing Intervention Start-dates

- Using the above rules for the handling of missing intervention start-dates, if the assumed intervention start-date:
 - is later than the reported intervention stop-date, the assumed intervention start-date will be reset and assumed to be the intervention stop-date.
- If, based on the above rules, it cannot be determined whether the intervention was taken prior to the study procedure, it will be assumed to be post-procedural.

Investigation of the Effect of Investigational Sites

As an exploratory analysis, the results by site will be examined: Small sites (i.e., sites that have less than 4 subjects) will be identified and the following method will be used for combining the data. Data from all small sites (<4 subjects) will be combined to form a single site in order to obviate non-estimable situations in the evaluation of site and site interaction effects. Once combined, the pooled site will remain as such for all analyses for which a site effect is determined. If the pooled smaller sites represent a single site that has more than twice as many subjects as the largest single site, however less than 3

times as many subjects, the small sites will be ranked by size and divided into 2 pooled assignments using an alternating sequence (ABABAB). If the pooled smaller sites represent a site that has more than three times as many subjects as the largest single site, however less than 4 times as many subjects, the small sites will be ranked by size and divided into 3 pooled assignments using an alternating sequence (ABCABCABC).

Imputation of Outcome Data

Missing data for subjects who fail to complete study follow-up without any evidence of a major stroke in the territory supplied by the treated artery or neurological death will be imputed in the analysis of primary safety using the multiple imputation procedure from SAS (Proc MI). Subjects who withdraw from the study prior to completion and have experienced a major stroke in the territory supplied by the treated artery or neurological death at any time will be counted as having experienced the event of interest. A separate tabulation will be provided based on the observed data: subjects who withdraw from the study prior to completion without any evidence of a major stroke in the territory supplied by the treated artery or neurological death will be counted as not having experienced the event of interest. For effectiveness, since follow-up imaging of the target aneurysm was not required at each study visit but was instead performed according to standard of care, the primary endpoint will be assessed using a selection rule, according to the following preferences:

- Imaging from day 141 (the opening of the 6-month follow-up window) onward is eligible to be included; imaging earlier than day 141 is disregarded for this analysis but imaging after the end of the 1 year window is still eligible.
- We will use the last adjudicated image at any time starting from day 141, UNLESS
- - o The last image is a CTA and there is a DSA within 90 days prior to the CTA, in which case the DSA will be used, OR
 - o The last image is an MRA and there is a DSA or CTA within 90 days prior to the MRA, in which case the DSA or CTA will be used. For this sub-rule we will prefer DSA over CTA if both exist.

The rules above define the available data for the purpose of endpoint calculations and effectiveness tables and listings. For subjects with no qualifying imaging per the above preference rules, multiple imputation will be employed to handle missing data for primary effectiveness.

In all cases, primary effectiveness will be defined according to the angiographic core laboratory's adjudication of images received.

Patient Accounting and study disposition

A complete accounting of patient participation in the study by analysis population will be presented in Table 14.1.1a entitled *Patient Accounting*. The purpose of this table is to provide an accounting of subjects from their entrance into the study through the final visit and to account for the evaluations of subjects in the analyses of efficacy and safety, including reasons for early study termination. The table will display the number of subjects that were consented and the number and percentage of subjects from the ITT, FAS, ICA, and non-ICA populations that:

- Underwent the study procedure (n/%)
- Evaluated at the 30-day follow-up visit (n/%)
- Evaluated at the 90-day follow-up visit (n/%)

- Evaluated at the 180-day follow-up visit (n/%)
- Evaluated at the 1-year follow-up visit (n/%)

The final study disposition of all subjects participating in the study by analysis population will be presented in Table form entitled *Patient Final Study Disposition*. A table entitled *Patient Accounting by Investigational Site* will follow a similar format and method of tabulation; however, this table will be presented by investigation site. A table entitled *Reasons for Screen/Implant Failures* will contain a tabulation of the number of subjects classified as screen/implant failures by individual reason.

A table entitled *Summary of Protocol Deviations* will contain a tabulation of the number and percentage of subjects from the ITT population with a deviation by deviation code. Multiple deviations per patient within the same category will only be counted once.

A listing entitled *Patient Disposition* supports various tables. This listing will be sorted by patient number. A listing entitled *Inclusion Criteria* displays the data from the Inclusion Criteria case report form. The data will be displayed for each patient and for each inclusion criterion. The listing will be sorted by patient number. A listing entitled *Exclusion Criteria* displays the data from the Exclusion Criteria case report form. The data will be displayed for each patient and for each exclusion criterion. The listing will be sorted by patient number. A listing entitled *Protocol Deviations* will list all protocol deviations for each patient. The listing will be sorted by patient number. The deviation code and description, visit and action, will also be included in the listing.

From the CRF, the following information will be presented in the listing:

- *What was the protocol deviation start date*
- *What was the associated visit*
- *What was the protocol deviation description*
- *What was the protocol deviation*
- *What was the reason for the protocol deviation*
- *Action taken? (Y/N)*
- *If action taken, please describe*

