The primary objective of this study is to assess the *outcomes* of the Pipeline™ Flex Embolization Device with Shield Technology™ in patients undergoing treatment for intracranial aneurysms in a large real-world, post-market setting. *Outcomes* will be assessed based on a series of standardized measurements recorded during the procedure and during the post-procedure follow-up period.

Attributes and parameters to characterize the outcomes of the Pipeline™ Flex Embolization Device with Shield Technology™ during the procedure will be addressed based on the following assessments (as observed):

- Successful deployment of the study device to the target site
- Implantation of the study device
- Entire IA neck covered by the study device
- Device malfunction during the delivery system preparation
- Adverse Events: By seriousness (Serious or Non-Serious) peri-procedural (Day 0), by relatedness (Procedure, Device and Anti-platelet therapy)

Attributes to characterize the outcomes of the study device post-procedure will be addressed based on the following assessments:

- Aneurysm occlusion (Class 1: Complete obliteration, Class 2: Residual neck, or Class 3: Residual Aneurysm)
- Adverse events: By Seriousness (serious and non-serious) ; per relatedness (procedure, device or antiplatelet therapy) and time of event (Acute 1-30 days, and Delayed 31-Study exit)
- Modified Rankin Scale (mRS)
- NIH Stroke Scale (NIHSS)
- Retreatment
- Major stroke in the territory supplied by the treated artery or neurological death
- Delayed Intracerebral hemorrhage (ICH) > 30 days post-procedure
- Parent artery stenosis (per Core Lab)
- Device migration (per Core Lab)

5. Investigation Plan

A prospective, single-arm, multi-center post-market observational study.

Up to 200 subjects who meet the Inclusion/Exclusion Criteria may be enrolled over a period of approximately 2 years to reach a target number of subjects. Study participation includes initial screening

and baseline evaluation, treatment using the Pipeline™ Flex Embolization Device with Shield Technology™, and follow-up visits at the discretion of the treating physician for 1 year beyond the index procedure. The total study duration is expected to be approximately 3 years.

Study Design:

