Subjects will be considered enrolled in the study once the patient has signed and dated the Informed Consent or DRF and the Pipeline™ Flex Embolization Device with Shield Technology™ is advanced into the micro catheter inside the patient. All enrolled subjects who underwent the study procedure and in whom an attempt to implant the device was made will be included in the analysis population.

A CEC will be in place for the study using a minimum of three physicians knowledgeable in the appropriate disciplines and medical specialties pertinent to the disease state being evaluated in this clinical study. This committee will be responsible for the review and adjudication to the study variables of all events identified in the CEC Charter/Manual of Operations.

The CEC will independently adjudicate to specified endpoint event definitions, event relatedness, event severity, and event outcomes.

The imaging core laboratory will be responsible for the qualitative image analysis to determine aneurysm occlusion, parent artery stenosis, and device migration. An imaging protocol will be provided to the site.

Pre-Specified Study Endpoints:

The pre-specified study endpoints and analysis listed here are the primary body of data that will be collected, analyzed, and summarized in a series of tables, lists, and graphs as part of the final report for this study. Other analysis will be conducted as part of the final report but these are the core set of analyses that will constitute the foundation of the clinical study report.

Primary endpoints:

Safety:

- Occurrence of major stroke in the territory supplied by the treated artery or neurological death post-procedure (1-year)

Effectiveness:

- Complete aneurysm occlusion (defined as Raymond-Roy grade 1) without significant parent artery stenosis ($\leq 50\%$) or retreatment of the target aneurysm post-procedure (1-year)

Secondary endpoints:

Safety:

- Occurrence of major stroke in the territory supplied by the treated artery or neurological death at 30 days post-procedure due to procedural complications
- Delayed intracerebral hemorrhage > 30 days post-procedure

Effectiveness:

- Device deployment success rate at the target site

Additional Safety Analyses:

- [REDACTED]
- [REDACTED]

- [REDACTED]
 - [REDACTED]
 - [REDACTED]

Additional Effectiveness Analyses:

- [REDACTED]
 - [REDACTED]
 - [REDACTED]
- [REDACTED]
- [REDACTED]
- [REDACTED]
- [REDACTED]
- [REDACTED]

Study Procedure:

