7.10 Safety Evaluation

All summaries of Adverse Events will be primarily reported, but not limited to, for the ITT population.

The Clinical Events Committee (CEC) will be responsible for the review and adjudication of all adverse events per the definitions established in the CEC Charter/Manual of Operations.

Site Reported and CEC adjudicated events shall be summarized in incidence and frequency tables coded by System Organ Class (SOC) and MeDRA preferred term (PT).

A table reporting CEC adjudication disposition will be presented (Site Reported, CEC adjudicated).

CEC adjudicated Adverse Events will be mapped to preferred terms and body systems using the Medical Dictionary for Regulatory Activities (MedDRA) coding dictionary. The number and percentage of subjects experiencing Adverse Events will be summarized by system organ class and preferred term for all Adverse Events.

CEC adjudicated Adverse Events will be presented by system organ class and preferred term.

Summaries of CEC adjudicated AEs by the maximal severity (Mild, Moderate and Severe), relatedness (e.g., to the study device, procedure, anti-platelet therapy.), seriousness (serious, non-serious) and timing (Peri-procedural- Day 0, Acute- day 1-30 and Delayed, Day 31-Study Exit) shall be presented.

Causality Assessment (Relatedness)

CEC adjudicated relationship of each adverse event will be presented as follows:

- Device: Medical device: (Medical device investigated in the Investigation)
- Procedure: The medical -surgical procedure on day 0
- Anti-platelet therapy: Related to the anti-platelet agent therapy, that is required per standard of care for treatment.

Missing and Partial Adverse Event Dates

The recorded dates for adverse events are important for an accurate tabulation of both events and patients, and required for the following:

1. Defining the start of the event
2. Designation of unique adverse event occurrences recorded intra-patient.

Completely missing or partially missing adverse event dates will be imputed as follows:

- If the adverse event start date is completely missing the adverse event will be counted to the date of the study procedure.
- If the adverse event start date is partially missing and the partial date is not sufficient to determine if the event occurred after the start of the study procedure, then the adverse event will be counted with a start date of the procedure date.

Summaries of Adverse Events

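### The SAP's earliest-date rule for incomplete adverse event dates can understate, and can never overstate, delayed intracerebral hemorrhage

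*SAP*

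**What the plan says.** SAP 7.4 gives four branches for an incomplete adverse event start date:

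- Nothing known: "If the entire Adverse Event start date is missing, then the procedure date will be used for the start date".
- Year only, same year as the procedure: "the year is the same as the year of the procedure then the procedure date will be used for the start date".
- Year only, later year: "If the year is greater than the year of the procedure, then January 1st will be used".
- Month and year known: "then the 1st will be used as the day of the start date unless the imputed date would be before the procedure". Events caught by that exception go to Day 0.

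SAP 7.10 restates the default: "If the adverse event start date is completely missing the adverse event will be counted to the date of the study procedure". It also assigns the procedure date to a partial date that cannot show whether the event followed the procedure.

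These dates feed outcomes that are defined by time. SAP 5 and 7.9 list "Delayed intracerebral hemorrhage > 30 days post-procedure" as one of two secondary safety endpoints. SAP 4 classifies post-procedure adverse events by "time of event (Acute 1-30 days, and Delayed 31-Study exit", and SAP 7.10 tabulates them by "timing (Peri-procedural- Day 0, Acute- day 1-30 and Delayed, Day 31-Study Exit".

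On who sets the date, protocol 8.1 includes the event start date among the items that the CEC adjudicates. The corresponding list in SAP 5 leaves it out.

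**The concern.** Whether an earliest-date rule is conservative depends on the outcome. For Day 0 and 30-day outcomes it can only add events, which is the cautious direction. For an endpoint with a lower time bound, such as hemorrhage after day 30, it can only remove them. The SAP applies one rule to both kinds and makes no exception for the delayed endpoint. Its worst-case and tipping-point analyses (SAP 7.9) cover primary effectiveness only.

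Late hemorrhage is likely to be a small count, so one relabelled event could be a large share of it. The predecessor post-market registry of the device without the surface treatment (ASPIRe, protocol 1.2.3) recorded 7 intracerebral hemorrhages among 191 subjects in total. The SAP introduction says the results may support a US indication evaluation, so the late-risk figure should not carry a one-sided error that is cheap to expose.

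**Working it through.** The documents give no delayed-hemorrhage rate and no number of incomplete dates, so there is no planned figure to reproduce. The check applies the four branches to true delayed events.

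**Inputs.** From the SAP: the 7.4 rules, the windows Day 0 / 1-30 / 31 to exit, 1 year of follow-up, at most 200 subjects, and two-sided 95% Clopper-Pearson intervals (SAP 6). Assumed: procedures on each day of a 365-day year, and true delayed events spread evenly over days 31-365 (335 days).

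**Direction.** In every case checked, the imputed date equalled the earliest possible day on or after the procedure and was never later than the true date. No true Day 0-30 event was moved past day 30. The delayed count can therefore fall or stay the same, but not rise.

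**Nothing known.** The imputed day is 0, so 100% leave the delayed window.

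**Year only.** The event goes to Day 0 if it falls in the calendar year of the procedure. For an event on day k that share is (365 − k)/365. The mean of k over 31-365 is 198, which gives (365 − 198)/365 = 167/365 = 45.8%. The event goes to Day 1-30 if 1 January falls on day 1-30, that is, for procedures on 2-31 December: 30/365 = 8.2%. Together 45.8% + 8.2% = 54.0%.

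**Month and year known.** An event on day 31 or later always lies in a later calendar month than the procedure, so it cannot be sent to Day 0. It moves to Day 1-30 only if the 1st of its month falls on or before day 30. A month has at most 31 days, so only events on days 31-60 can be affected. Enumeration gives 49.1% of events on those 30 days, an average of 0.491 × 30 = 14.7 days per procedure date. Over the whole delayed period this is 14.7/335 = 4.4%.

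| Known date parts | To Day 0 | To Day 1-30 | Stays delayed | Leaves the window if true day is 31-60 |
|---|---|---|---|---|
| None | 100% | 0% | 0% | 100% |
| Year only | 45.8% | 8.2% | 46.0% | about 96% |
| Month and year | 0% | 4.4% | 95.6% | about 49% |

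**Examples.** Procedure on 10 March, hemorrhage on 25 April (day 46). With the day missing it is dated 1 April (day 22, acute). With the month also missing it is dated Day 0. For a hemorrhage on 20 June (day 102) with the day missing, the imputed date is 1 June (day 83), still delayed.

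**Effect of one event at N = 200 (counts are illustrative).**

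| Delayed count if one event is lost | 95% CI | Count if it is kept | 95% CI |
|---|---|---|---|
| 0/200 (0.0%) | 0.00-1.83% | 1/200 (0.5%) | 0.01-2.75% |
| 2/200 (1.0%) | 0.12-3.57% | 3/200 (1.5%) | 0.31-4.32% |
| 4/200 (2.0%) | 0.55-5.04% | 5/200 (2.5%) | 0.82-5.74% |

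**The case against.** The best defence is that the rule will seldom or never touch this endpoint. Serious events are reported within 24 hours of awareness, with source documents requested (protocol 6.2). Subjects are contacted at about 1, 3, 6 and 12 months (protocol 5.5). The CEC adjudicates start dates and can ask for records and imaging (protocol 8.1), and SAP 7.13.3 has it adjudicate late intracerebral hemorrhage. Imputed values are already flagged in the listings (SAP 7.2.1), so a relabelled event could be traced. In the predecessor registry most major events came within 30 days, so an undated hemorrhage may well be early. The study is descriptive, and no threshold is set for this endpoint.

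Most of this stands, and it keeps the point small. It does not settle which date is used: SAP 5 omits start date from the CEC's tasks, and neither 7.4 nor 7.10 says that an adjudicated date takes precedence over imputation.

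Three stronger readings are tempting but unsupported:

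- That the endpoint is understated. This needs a delayed hemorrhage whose date is still incomplete at database lock, and the documents do not show that one will exist.
- That about 96% of delayed events with the day missing are lost. That figure holds only for events in the calendar month right after the procedure, where 49.8% are truly beyond day 30 and 1.9% are imputed so. Over days 31-365 the loss is 4.4%.
- That delayed events will generally appear as peri-procedural. Only a missing month, or a wholly missing date, can send one to Day 0.

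**Conclusion.** The concern holds as a one-sided possibility, and it is minor. The rule can lower the delayed-hemorrhage endpoint and the Delayed tables but cannot raise them. The 100%, 54% and 4.4% are shares of true delayed events with each kind of incomplete date, and they rest on even timing over days 31-365. If events cluster on days 31-60, the shares become 100%, about 96% and about 49%. None of them estimates the actual bias, because the number of incomplete dates is unknown and possibly zero.

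Only the window label is at risk. The primary safety composite at 1 year and the count of all intracranial hemorrhages through 1 year (SAP 7.9) do not change, and the rule remains cautious for Day 0 and 30-day outcomes.

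**What to change.** In SAP 7.4 and 7.10:

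1. State that the CEC-adjudicated start date (protocol 8.1) governs all timing endpoints, and that imputation applies only where that date is still incomplete. Add start date to the CEC list in SAP 5.
2. Keep the earliest-date rule for Day 0 and 30-day outcomes.
3. For delayed hemorrhage, report beside the main result a sensitivity count, with its Clopper-Pearson interval, in which any hemorrhage whose known date parts allow a date after day 30 is counted as delayed.

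The third item should stay a sensitivity count. As the main rule, treating such events as delayed unless shown otherwise would only reverse the bias and could place one event in two windows that are meant to be exclusive.

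The cost is a few sentences of SAP text, one extra table row and a footnote. No new flagging is needed, since SAP 7.2.1 already provides it.
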